### **Recruitment/randomization**

In addition to recruitment by rural clinic personnel, we will also recruit using flyers posted in rural communities and media advertising including print, radio and Facebook®. We will recruit at least 50% females and minorities to reflect or exceed minority representation in rural Kansas (16.7%) (49). Potential participants will be asked to contact study staff via phone, email or our laboratory web site. Interested individuals will be directed to complete a brief web-based screener on our laboratory website, or will be interviewed by phone, to assess self-reported height and weight (BMI), medication use, presence of chronic disease, smoking habits, previous attempts at weight loss, and current level of PA. Those satisfying the initial eligibility criteria will be scheduled to attend an in-person meeting with study staff at the participant's respective clinic. At this session staff will describe the project, answer questions, obtain consent, complete eligibility screening surveys, and measure height and weight to determine preliminary eligibility based on BMI. Screening surveys including health history, depression, eating behavior and binge eating will be administered using web-based software (Research Electronic Data Capture software (REDCap), Vanderbilt University, Nashville, TN) (50). These surveys will be completed during the in-person meeting or at home, depending on the availability of home internet access. Project staff will then send a form (fax/email) to the potential participant's primary care physician describing the study and requesting clearance for participation. Final eligibility based on BMI will be confirmed at baseline testing, using height and fasting weight assessed with participants wearing hospital gowns. Participants in each clinic will be randomized, stratified by sex, to one of the three study arms. The randomization sequence will be generated by an independent statistician, sent to the project coordinator and concealed until intervention groups are assigned.

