### **Outcome assessments.**

Outcomes will be obtained at each participating clinic. As outlined in Table 3, most outcomes will be assessed at 0, 6, 12, and 18 months. Physical measures, i.e., height, weight, waist circumference, and blood pressure, will be obtained between 7-11 a.m., following a minimum 12-hour fast, by trained research assistants blinded to condition. Research assistants will receive refresher training and complete reliability assessments for physical measures two to three times each year.

**Anthropometric measures.** Weight will be measured with a digital scale accurate to  $\pm 0.1 \text{ kg}$  (Befour Inc. #PS6600, Saukville, WI) with participants in a hospital gown. Height will be measured with a stadiometer (Model #IP0955, Invicta Plastics Limited, Leicester, UK). The average of two measures within 0.25 cm will be recorded. Body mass index (BMI) will be

calculated as weight (kg) divided by height ( $m^2$ ). Waist circumference will be measured with an anthropometric tape using the procedures described by Lohman et. al. (72). Three measurements will be obtained with the outcome recorded as the average of the closest 2 measures.

**Blood chemistry/ blood pressure.** Fasting blood samples will be obtained by a clinic phlebotomist. Analysis of HDL and LDL cholesterol, triglycerides, glucose, and HbA1c (diabetics) will be completed by the commercial laboratories that are contracted by each participating clinic. Blood pressure will be obtained in duplicate, with an automated sphygmomanometer (DinaMap ProCare 100, General Electric Healthcare, Chicago, IL) using the National Health and Nutrition Examination Survey (NHANES) blood pressure protocol (73).

**Compliance with diet recommendations.** Energy and macronutrient intake will be assessed using the self-administered, web-based VioScreen Graphical Food Frequency System (Viocare Technologies, Inc., Princeton, NJ). Participants will complete the survey at a computer in a private room during the clinic assessment visit, or at home on a tablet or personal computer within one or two days following the clinic visit. Participants who fail to complete the survey within that time frame will receive email and telephone reminders. Assessment of nutrient intake using VioScreen is correlated with assessments obtained from a traditional paper and pencil food frequency questionnaire: total fat = 0.82, saturated fat = 0.84, protein = 0.67, carbohydrate = 0.79, alcohol = 0.90 (74).

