assuming an autoregressive correlation structure of weight over time, controlling for baseline weight, treatment group and time as covariates. The global comparison across the three arms will be followed by two pairwise comparisons of interest, i.e., IP versus EUC, and GP versus IP. Independent comparisons of change in each chronic disease risk factor, i.e., waist circumference, triglycerides, HDL cholesterol, blood pressure, and fasting glucose at 6, 12, and 18 mos., across the 3 intervention arms will be completed using a mixed linear model, assuming an autoregressive correlations structure. We will also compare Quality of life (SF-36), daily stress associated with eating (Nutrition Hassles Questionnaire), self-efficacy for weight change (WELS), self-efficacy for exercise (EXES), and self-efficacy for overcoming barriers to exercise (BARSE) among the three intervention arms across 24 months using a using a mixed linear model assuming an autoregressive correlation structure both unadjusted and adjusted for covariates. A variety of exploratory analyses, as deemed appropriate by the principal investigator and the project biostatistician, e.g., assessment of the impact of health educator absences and turnover, community environment for healthy eating and PA etc. on weight loss outcomes, will be performed. Analyses will be completed using SAS version 9.4 or higher.

**Missing data.** We will determine if the proportion of participants lost to follow-up differs by intervention arm and/or sex, and compare demographic characteristics between those lost to follow-up and completers. If there are differences across treatment groups, we will examine demographic characteristics, i.e., sex, age, magnitude of weight loss, between completers and those lost to follow-up, to determine if there are significant differences ( $p < 0.05$ ) in those characteristics. If missing data are related to intervention group and/or demographic characteristics, we will use model based multiple imputation; otherwise, traditional multiple imputation will be used.

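### The risk-factor models analyse change and name no covariate; adding the baseline value, clinic and sex would make these secondary comparisons more precise and their standard errors better calibrated, at no cost in data.

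*Combined protocol and SAP*

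**What the plan says.** All the modelling statements are in *Statistical power and analysis*, Analysis plan.

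- **Risk factors** (waist circumference, triglycerides, HDL cholesterol, blood pressure, fasting glucose): "Independent comparisons of change in each chronic disease risk factor" at 6, 12 and 18 months "across the 3 intervention arms will be completed using a mixed linear model, assuming an autoregressive correlations structure". No covariate is named.
- **Weight over 24 months**, just before: a mixed model "controlling for baseline weight, treatment group and time as covariates".
- **Questionnaires**, just after: "both unadjusted and adjusted for covariates", without saying which covariates.

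Neither of the last two statements extends to the risk factors.

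On allocation, *Recruitment/randomization* says: "Participants in each clinic will be randomized, stratified by sex, to one of the three study arms". Clinic and sex are named as covariates in no efficacy model. The only adjustment for clinic is in the contingent valuation analysis (*Cost considerations*, Cost analysis).

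*Study Overview* lists the risk factors as a secondary comparison, and *Outcome assessments* has most outcomes measured at month 0 as well as at 6, 12 and 18 months.

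**The concern.** Two separate things are left out, and they have different consequences.

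**Baseline value.** An unadjusted change score fixes the coefficient on baseline at 1. For a variable with regression to the mean the best coefficient is below 1, so subtracting the whole baseline adds noise that a covariate would remove. This is a real loss of precision in the estimated arm difference.

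**Clinic and sex.** Allocating within clinic-by-sex strata makes the arms alike on both factors, so the arm difference already benefits from that balance. A model without them leaves their variation in the residual and reports a standard error larger than the true one. Intervals are then too wide and tests conservative.

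At stake is the usefulness of the risk-factor results. No power is stated for them, and the EUC arm has only 40 participants, or 32 after the 20% loss that the plan allows for.

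**Working it through.** **Inputs from the plan.** 200 participants, 80/80/40; about 40 per clinic from at least five clinics; allocation within clinic by sex; risk-factor tests at 0.05. The documents give no baseline/follow-up correlation r, and no share of variance due to clinic or sex, for any risk factor. Both are assumed below and shown as ranges.

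**1. The plan's own figures.** Power is stated only for 6-month weight loss. With SD 7 kg for change and two-sided alpha of 0.025 (the plan does not state sidedness), a noncentral t calculation gives:

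| Comparison | Difference | Standard error, all randomised | Power, all (stated) | Power, 20% loss (stated) |
|---|---|---|---|---|
| IP vs EUC | 6 kg | 7·√(1/80+1/40) = 1.356 | 98.4% (98%) | 95.2% (95%) |
| GP vs IP | 4 kg | 7·√(1/80+1/80) = 1.107 | 91.1% (91%) | 83.1% (83%) |

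These figures reproduce. They rest on the SD of weight change, so nothing below alters them.

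**2. Baseline value.** Take one follow-up visit, with the same SD, s, at baseline and follow-up.

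- Variance of a change score: 2(1−r)s²
- Residual variance with baseline as covariate: (1−r²)s²
- Ratio: (1−r²) / [2(1−r)] = (1+r)/2

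| r (assumed) | Variance ratio | SE ratio | Change-score sample giving the same precision (200/ratio) | Power if change scores give 80% |
|---|---|---|---|---|
| 0.5 | 0.75 | 0.866 | 267 | 90% |
| 0.7 | 0.85 | 0.922 | 235 | 86% |
| 0.8 | 0.90 | 0.949 | 222 | 84% |
| 0.9 | 0.95 | 0.975 | 211 | 82% |

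The last column is Φ[(1.960+0.842)/√ratio − 1.960], at two-sided 0.05. For example, at r = 0.5: 2.802/0.866 − 1.960 = 1.275, and Φ(1.275) = 0.90. The ratio is below 1 for every r below 1.

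**3. Clinic and sex.** If together they explain a share R² of the residual variance, including them multiplies the reported standard error by √(1−R²). For an assumed R² of 1% to 10%, that is 0.995 to 0.949.

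To separate reported from true precision, a simulation used five clinics of 40, exact 8/8/4 allocation in each clinic-by-sex stratum, one follow-up visit, r = 0.7 and 2,500 runs. The assumed effects, in SD units, were a clinic effect with SD 0.2 at follow-up, a sex difference of 0.5 at baseline, and a further sex effect of 0.2 at follow-up. There was no laboratory effect. For the IP–EUC contrast:

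| Model | True sampling SD | Mean reported SE |
|---|---|---|
| Change, no covariates | 0.1484 | 0.1540 |
| Change + clinic + sex | 0.1484 | 0.1500 |
| Baseline only | 0.1379 | 0.1441 |
| Baseline + clinic + sex | 0.1378 | 0.1387 |

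- Adding clinic and sex leaves the true variability where it was (0.1484 to 0.1484; 0.1379 to 0.1378).
- Without them the reported SE is too large by about 4% (0.1540/0.1484 = 1.04; 0.1441/0.1379 = 1.045). With them it is within about 1%.
- Baseline gives the real gain: 0.1379/0.1484 = 0.93, close to the 0.922 in step 2.
- With all three terms the reported SE falls about 10% (0.1387/0.1540 = 0.90).

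**The case against.** **The plan is silent; it does not omit.** The risk-factor sentence lists no model terms, not even arm and visit, which must be there. It may be shorthand. That stands: the accurate statement is that covariates are not named. But the neighbouring weight model does name its baseline, and an unstated covariate set can be chosen after the data are seen.

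**Change scores are valid.** Under randomisation the unadjusted comparison is unbiased, and regression to the mean acts on all arms alike in expectation. This also stands. The point concerns efficiency and the calibration of standard errors, in secondary outcomes with no power claim.

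**The size is assumed.** Correct. On the standard-error scale the baseline gain is 13% to 5% at r of 0.5 to 0.8, and under 3% at r = 0.9.

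**The scope is narrow.** No efficacy model names clinic or sex, the primary t-tests included. True; this point makes its claim only for the risk factors.

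**Stronger readings that a reader might infer.**

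- *Laboratory differences between clinics add noise.* *Outcome assessments* says that the blood analyses "will be completed by the commercial laboratories that are contracted by each participating clinic". It does not say that the laboratories differ, so clinics might share one, and no calibration difference or change of laboratory is mentioned. A constant offset cancels in a change score: adding one to a simulation without clinic or sex effects at follow-up left the reported SE at 0.150. The argument could not reach waist or blood pressure in any case, since these are taken "by trained research assistants blinded to condition". It forms no part of this point.
- *Leaving out clinic and sex makes the estimates themselves less precise.* With allocation balanced within strata it hardly does; it mainly inflates the reported standard error.
- *The weight result is undermined.* It is not. The weight power reproduces and does not depend on the risk-factor models.

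**Conclusion.** The point holds as a free improvement to a secondary analysis. As written, the risk-factor models use change and name neither the baseline value nor the two factors used in randomisation. Adjusting for baseline would cut the variance of an arm difference by 25% to 10%, and its standard error by about 13% to 5%, for r between 0.5 and 0.8. Naming clinic and sex would mainly bring reported standard errors down to their true size, by roughly 0.5% to 5% if the two explain 1% to 10% of residual variance.

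These sizes rest on assumed r and R², equal variances at baseline and follow-up, and close balance within strata. The direction does not depend on the particular value of r. The documents do not support a finding of bias, of inflated type I error, or of any effect on the stated power for weight.

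**What to change.** Replace the risk-factor sentence with an explicit model. For each risk factor, analyse the 6, 12 and 18 month values in the mixed linear model with baseline value, clinic (fixed effect), sex, arm, visit and arm-by-visit. Once baseline is a covariate, using the value or the change as the outcome gives the same arm differences, so results can still be reported as change.

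The cost is wording in the analysis plan. Baseline values are collected at month 0, and clinic and sex are known at randomisation. No further data, visits or participants are needed.
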